# 1) Completely missing AE end dates

When an AE end date is missing but there is another AE occurrence with the same lowest level term (LLT) and onset date and with an end date, this end date will be used for the imputation.

Otherwise, the imputation rules described in the Table 6.6: 1 are used.

Table 6.6: 1 Algorithm for missing AE end date

Outcome of event	Action
Patient died	Impute all missing AE end dates with date of death
Patient did not die	If follow-up performed, impute missing AE end date for on-going AEs with the latest follow-up date.  Otherwise, impute missing AE end date with the date of the last available visit.

# 2) Missing/partial AE onset date

## Step 1

For each missing or partial AE onset date, a time-interval (O1 - O2) has to be defined as follows:

If AE onset date is missing then:

- O1 = minimum between AE end date and date of informed consent
- O2 = minimum between AE end date and date of last visit

# If AE onset date is partial:

- O1 = minimum between AE end date and First Possible onset date
- O2 = minimum between AE end date and Last Possible onset date

For the definition of this time-interval only, partial AE end date must be **initially** imputed as Last Possible end date.

## Step 2

Then the AE onset date is imputed according to the rules described in Table 6.6: 2.

Table 6.6: 2 Algorithm for missing or partial AE onset date

Condition	Action	
Date of first drug administration > O2	Impute onset date with O2	
O1 ≤ Date of first drug administration ≤ O2	Impute onset date with date of first drug administration	
Date of first drug administration < O1	Impute onset date with O1	

## 3) Partial AE end date

# Step 1

For each partial AE end date, a time-interval (E1- E2) has to be defined as follows:

E1 = maximum between AE onset date and First Possible end date

E2 = maximum between AE onset date and Last Possible end date

## Step 2

Then the AE end date is imputed according to the rules described in Table 6.6: 3.

Table 6.6: 3 Algorithm for partial AE end date

Condition	Action
Date of first drug administration > AE onset date and patient died	Impute end date with minimum (E1, date of death)
Date of first drug administration > AE onset date and patient did not die	Impute end date with minimum (E1, last visit date including follow-up visits)
Date of first drug administration ≤ AE onset date and patient died	Impute end date with minimum (E2, date of death)
Date of first drug administration ≤ AE onset date and patient did not die	Impute end date with minimum (E2, last visit date including follow-up visits)

Partial or missing information on the date of first administration of trial drug

If patients have been randomised but not treated, no imputation will be done for the date of first administration of trial drug. Patients are considered randomised but not treated if they have been randomised, no administration has been done during the visits, and the number of kits dispensed equals the number of kits returned.

Otherwise, if the date of first drug administration is missing but the patient was randomised and treated, the date of the first drug administration will be set to the date of kit dispensation.

For partial date of first drug administration, if only the year is present and equal to the year of the randomisation date, the first drug administration will be set to the date of randomisation. If only the day is missing (month and year present), if randomisation was in the same month and year, then the first drug administration will be set to the date of randomisation. If randomisation was in the month prior to the first drug administration the missing day will be imputed as the first day of the month.

Missing information on the time of administration of trial drug

A missing time of first drug administration will be imputed as 12:00 o'clock noon. Missing administration times at on-treatment visits will be imputed by 8:00 o'clock in the morning.

Partial or missing information on the date of last administration of trial drug

If this date is partial or missing, the date will be imputed by the date of the respective visit, if available.

If the date is partial with only month and year and the visit date is missing, it should be the last day of this month.

If a patient is lost-to-follow up and no date of last drug administration is reported, the date of last drug administration is set as the date of last contact.

For a patient who dies in the treatment phase, the date of last drug administration is set as the date of death, assuming that the patient took the medication until the date of death.

Rules following this are described in Section 6.1. All other cases need to be assessed by the trial team on an individual basis, trying to use the points above as guidance.

Partial or missing information on the date of administration of trial drug (excluding first and last administration)

If any such date is missing, it will be imputed by the respective visit date.

If month and year are available and equal to the visit date, the date is imputed by the day of the respective visit. If month is later than the month of the visit date, the day will be imputed by the 1st of the month.

Missing information on the birth date

If only the year of birth is known, the day and month of birth will be imputed as 01 January.

Missing information on concomitant therapy dates

For incomplete date information always the midpoint of the possible interval will be used. If only the year is present the day and month will be imputed as 01 July, if year and month is present the day will be imputed as 15. If the year is missing, the date will be considered missing.

If this leads to contradictions for the start or end date of a concomitant therapy (e.g. imputed end date before documented start date) a partial end date will be imputed as the end of the interval or a partial start date will be imputed as the start of the interval in the database to resolve this contradiction.

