## FLOW CHART

Trial period	Screening	Treatment period						FU
		2	3	4	5	6 to N	EOT C	
Visit	1							
Week	-2	0	12	36	60	84 to N B	-	-
Days from randomization	-14 A	0	84	252	420	588 to N B	-	EOT + 30
Time window (days) O	+13 A		±7	±14	±14	±14	±14	+7
Informed consent	X							
In/exclusion criteria	X	X						
Medical history/ concomitant diagnoses	X							
Demographics	X							
Physical examination F		X		X		X	X	X D
Vital signs	X	X	X	X	X	X	X	X D
Height	X E							
Weight	X E			X	X	X	X	
Waist circumference		X		X	X	X	X	
12-lead-ECG H		X		X	X	X	X	X D
Pregnancy Test I		X		X	X	X	X	
Fasted home blood glucose monitoring J		X	X	X	X	X	X	
Safety laboratory K	X	X	X	X	X	X	X	X D
UACR Q	X	X A		X		X K	X	X D
HbA 1c	X	X	X	X	X	X	X	
Lipid panel		X		X		X K	X	X D
eGFR L	X	X	X	X	X	X	X	X D
Pharmacogenetic sampling P		X						
Adverse events/outcome events M	X	X	X	X	X	X	X	X
Concomitant therapy	X	X	X	X	X	X	X	X
Randomization (IRT) N		X						
Dispense study medication (IRT) N		X	X	X	X	X		
Return study medication/ medication compliance check			X	X	X	X	X	

Proprietary confidential information.

© 2016 Boehringer Ingelheim International GmbH or one or more of its affiliated companies. All rights reserved.

This document may not - in full or in part - be passed on, reproduced, published or otherwise used without prior written permission.

Flow Chart (continued)

A Randomization may be done as soon as the visit 1 (safety) laboratory results and eGFR are known and all other eligibility criteria are met. If the UACR result at visit 2 is required to fulfil inclusion criterion 8, randomization may be postponed until the laboratory results are known. It's not required to repeat visit 2 assessments if the patient returns to the clinic for randomization.

B A clinic visit will be scheduled every 24 weeks until study end.

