N Interactive Response Technology (IRT) will allocate medication kit numbers at all study visits from visit 2 till study end. At visit 2 patients will receive one treatment box sufficient for 12 weeks treatment (plus one week reserve). As of visit 3 patients will receive two medication boxes sufficient for 24 weeks treatment (plus two weeks reserve).

O The protocol allows a time window of +/- 7 days for visit 3 and +/- 14 days for all scheduled visits in the treatment period after visit 3. To ensure sufficient medication, visits after visit 3 should be scheduled within 182 days and visit 3 should take place no later than 91 days after visit 2.

P To allow possible retrospective pharmacogenetic analyses, all patients eligible for randomization will be asked for a blood sample with a separate informed consent. The pharmacogenetic sample should preferably be taken at visit 2, but could also be taken at any later visit, depending on availability of the respective informed consent. Pharmacogenetic sampling is voluntary and is not a prerequisite for participation in the study.

Q Urine Albumin Creatinine Ratio (UACR) will be calculated at the central lab, and should be measured on a first morning void specimen wherever possible.

Proprietary confidential information.

© 2016 Boehringer Ingelheim International GmbH or one or more of its affiliated companies. All rights reserved.  
This document may not - in full or in part - be passed on, reproduced, published or otherwise used without prior written permission.

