### 3. DESCRIPTION OF DESIGN AND TRIAL POPULATION

#### 3.1 OVERALL TRIAL DESIGN AND PLAN

This randomized, double-blind, and placebo controlled study compares treatment with linagliptin (5 mg once daily) with placebo treatment (matching tablets once daily) as add-on therapy to standard of care background antidiabetic treatment as specified in [Section 3.3.2](#).

The trial is event driven and will run until 625 **611** patients with a by adjudication confirmed primary endpoint event are observed ([Section 7.6](#)), with an estimated 8300 **7000** randomized patients to be observed for an estimated study duration of 48 **54** months, beginning with the randomization of the first patient. The anticipated recruitment period is 36 months. In case the number of primary endpoint events is not or may not be reached within this period the trial duration ~~and/or the number of patients~~ will be increased until the defined number of adjudicated primary endpoint events is reached.

[figure not shown]

Figure 3.1: 1 Treatment periods and treatment groups in the trial design

For all patients, site visits are scheduled at regular time intervals (see [flow chart](#)). The estimated treatment duration for the first randomized patient is 48 **54** months. The number of confirmed adjudicated primary endpoint events will be continuously monitored during the trial. Based on the available number of events the projected number of expected future events will be calculated. As soon as the projection reliably suggests that the total number of patients with a by adjudication confirmed primary endpoint event will reach **625 611** ~~within the next 24 weeks~~, the trial team will perform respective actions to stop the trial. From this time point on, all patients are expected to perform their last visit (EOT visit) within the ~~regular proposed~~ time schedule, which means ~~within the next 24 weeks~~ **communicated via an investigator letter**.

The End of Treatment visit (EOT) activities will be performed when a patient discontinues study medication treatment permanently. The EOT activities are not required for temporary interruptions of study drug. All patients will have a follow up visit ~~one week~~ **30 days** following discontinuation of study drug, irrespective whether they complete the treatment period or pre-maturely discontinue study treatment. Patients who discontinue study drug prematurely should continue study visits until study end. Study assessments may be omitted

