## 6.8.3 Censoring

Primary endpoints

The underlying principle is that the censoring date should be the date at which the patient was last known to be free of an endpoint event (e.g. free of each component of the 3P-MACE).

Patients without occurrence of a specific endpoint (composite endpoint or individual components) will be considered censored at the individual day of trial completion\*.

- \* This is defined as the latest of the following dates as of
  - adverse event/outcome event start dates (if non-fatal event),
  - onset dates of adjudicated (by adjudication confirmed and non-confirmed) events (if non-fatal event),
  - date of trial completion (defined as latest of date of last clinic visit, last telephone contact, date of last contact if lost to follow-up).

For patients who died during the study, the date until which follow-up for non-fatal outcome events was performed will be used for censoring.

Censoring is considered independent from trial drug intake.

Generally, the 7 days censoring definition will be used for adverse events incl. hypoglycaemia.

All of the above mentioned x-day censoring rules will be handled as follows:

Patients who did not experience the event will be censored at the earliest date between the individual day of trial completion (defined above) and x days after last intake of study drug. For this analysis events will be considered that occurred not later than x days after last intake of study drug, or until individual day of trial completion (defined above), whichever is earlier.

Endpoints based only on laboratory data (by adjudication confirmed or not)

Patients who already fulfil the respective condition at baseline are generally not considered in the number of patients at risk for this endpoint (

If a baseline laboratory measurement is not available for the parameter of interest, it is assumed that the patient did not experience the condition corresponding to the endpoint at baseline and the patient is included in the patients at risk for this endpoint.

Patients without an event and available post-baseline laboratory measurements will be considered censored at the date of last laboratory sampling of the corresponding parameter. Patients with missing baseline laboratory required to derive a change from baseline and patients without laboratory data following the baseline measurement will be censored on the day of randomisation or date of first study drug intake, respectively.

Page 51 of 80

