#### 7.8.1.1 Assignment of AEs to treatment

The analysis of AEs will be based on the concept of treatment-emergent adverse events (TEAE). That means that all AEs occurring between first study drug intake until 7 days after last permanent study drug stop will be considered as on-treatment, i.e. possible treatment interruption phases of a patient will be part of the on-treatment phase.

All AEs occurring prior to first study drug intake will be assigned to "screening". All AEs occurring after last study drug intake + 7 days will be assigned to "post-treatment", whereby the post-treatment phase according to the previous treatment will be used (post-Lina and post-Placebo respectively). AEs reported after the date of last contact + 1 day will be assigned to "post-study".

Patients who died before last drug intake + 7 days will have their on-treatment phase assigned until the date of death.

In addition to the primary treatment emergent approach displaying the on-treatment phase and post-treatment phase separately, all AEs after the first dose of study medication will be included in an additional analysis by treatment group.

Further additional approaches will be implemented for the presentation of adverse events:

• For cancer and pancreatic cancer in addition to the 'TEAE approach' on the treated set, all adverse events that occurred between first study drug intake up to study end will be presented.

There will be additional analyses including all patients who had a minimum cumulative study drug exposure of 6 months (excluding treatment gaps), using following two approaches:

- o considering all AEs starting from the date when 6 months cumulative exposure was reached up to last drug stop + 7 days
- o considering all AEs starting from date when 6 months cumulative exposure was reached up to individual day of trial completion
- For renal events, hepatic events, pancreatitis and skin lesions all adverse events that occurred between first study drug intake up until treatment stop + 30 days will be presented based on the treated set.
- Heart failure adverse events (based on narrow SMQ cardiac failure 20000004) will be analyzed following the 'TEAE approach' (all AEs occurring between first study drug intake until 7 days after last permanent study drug stop will be considered as ontreatment) and the concept where all AEs from first study drug intake up to study end are assigned to treatment.

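### SAP 6.6 replaces a partial last-dose date with the visit date even when the recorded month and year are earlier, so some patients count as on treatment for too long

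*SAP*

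**What the plan says.** SAP 6.6, on the date of last administration of trial drug, treats partial and missing dates alike: "If this date is partial or missing, the date will be imputed by the date of the respective visit, if available". The known month comes in only as a fallback: "If the date is partial with only month and year and the visit date is missing, it should be the last day of this month". Nothing requires the visit to fall in the recorded month, and nothing caps the imputed date at the end of that month. Separate rules cover patients lost to follow-up with no last-dose date and deaths in the treatment phase. Individual assessment by the trial team is reserved for cases that these rules do not cover.

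For administration dates other than first and last, the same section does compare months: "If month and year are available and equal to the visit date, the date is imputed by the day of the respective visit".

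The last-dose date is then used in several places:
- SAP 7.8.1.1: "all AEs occurring between first study drug intake until 7 days after last permanent study drug stop will be considered as on-treatment". A +30-day window applies to renal events, hepatic events, pancreatitis and skin lesions.
- SAP 7.8.1.5.2: adverse event time at risk ends x days after last intake, or at death.
- SAP 6.8.3, x-day rules, where x counts the days from the final dose: "Patients who did not experience the event will be censored at the earliest date between the individual day of trial completion (defined above) and x".
- Protocol 7.3.1: on-treatment + 30 days sensitivity analyses of the primary and key secondary endpoints.

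**The concern.** The rule discards information that bounds the answer. Take a last dose recorded as March 2015, day unknown, with a visit on 20 July 2015. The rule gives 20 July. The same record with no visit date gives 31 March, so having more information yields a worse date.

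Where this happens, time and events known to be off drug are assigned to treatment. On-treatment adverse event counts and person-time both grow, and the contrast between arms is diluted. In a non-inferiority trial the on-treatment analyses are a main check on dilution by off-drug time, so adding such time to them weakens that check.

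**Working it through.** The plan states no figure for this rule, so there is none to reproduce. The check is date arithmetic.

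**Inputs**
- Imputed date under the rule: the visit date V (SAP 6.6).
- Latest date consistent with the record: U = min(last day of the recorded month, V).
- Visit spacing: "A clinic visit will be scheduled every 24 weeks until study end" (Protocol flow chart), i.e. 24 × 7 = 168 days. The same chart notes that "visits after visit 3 should be scheduled within 182 days". Visit 3 is 84 days after randomization.
- Delay from last dose to the respective visit: not stated. **Assumption:** uniform over 0 to L days, with L varied. Visit dates are spread over a full year.

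**Formula.** Excess contradicted by the record = V − U. It is zero when the visit falls in the recorded month.

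**Single case.** V = 20 July 2015 and U = 31 March 2015, so the excess is 30 + 31 + 30 + 20 = 111 days (April, May, June, and July to the 20th).

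**Averages over all visit dates and delays**

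| Visit within L days of the stop | Visit in a later month | Mean excess (days) | Excess > 7 days | Excess > 30 days |
|---|---|---|---|---|
| 14 | 23% | 1.2 | 6% | 0% |
| 28 | 46% | 4.6 | 26% | 0% |
| 56 | 72% | 16.0 | 60% | 20% |
| 84 | 81% | 29.1 | 73% | 46% |
| 168 | 91% | 70.2 | 87% | 73% |
| 182 | 91% | 77.1 | 88% | 75% |

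**Check on the 168-day row.** The mean gap from true stop to visit is 168/2 = 84.0 days. The mean gap from true stop to U is 13.8 days. The difference is 84.0 − 13.8 = 70.2 days. The full 84 days is not the right measure of the error, because about 14 of them cannot be ruled out from a month-and-year record.

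**Effect on set membership.** Protocol 7.3 requires at least 30 days of treatment for the on-treatment set. Suppose randomization and first dose are on 10 March, the last dose is recorded as March, and visit 3 is on 2 June. The record allows at most 31 − 10 + 1 = 22 days of treatment. The rule gives 22 + 30 + 31 + 2 = 85 days (March, April, May, June), so a patient who cannot qualify would be included.

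**What is not touched.** SAP 7.4.1 counts all events to trial end, and SAP 6.8.3 makes the main censoring independent of drug intake. The primary non-inferiority test does not use the last-dose date.

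**The case against.** The strongest reply is about size. Protocol 3.1 ties a visit to stopping: "The End of Treatment visit (EOT) activities will be performed when a patient discontinues study medication treatment permanently". The flow chart places follow-up 30 days after that visit, and section 3.1 places it 30 days after drug discontinuation; the two agree only if the visit is close to the stop. If the respective visit is a prompt end-of-treatment visit, the first two rows of the table apply and the excess is a few days at most on average. This stands as the planned course, but not as a guarantee. No maximum delay is stated and the term is not defined in the public text. Protocol 3.3.4.1 also allows interruptions without limit in number or length, so a stop may be recognised as permanent long after the last dose.

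Second, the adverse event on-treatment phase deliberately includes treatment interruptions, and all events after first dose are also displayed without a last-dose cut-off. A few imputed dates add little to that, and a longer window keeps late events rather than dropping them. This limits the consequence. It does not justify a date that the record excludes.

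Third, queries are to be resolved before database lock, which should leave few partial dates. That is fair, and no affected patient can be shown from the documents.

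A reader might also infer from the intermediate-dose rule that the authors plainly did not intend to overrule a known month. The text does not go that far: that rule covers a month equal to or later than the visit month and is silent on an earlier one, which is the only case at issue.

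**Conclusion.** The rule is wrong as written. It can produce a last-dose date that the patient's own record contradicts, and individual review does not reach the case. It applies only to patients with a partial last-dose date, an available visit date and a visit in a later month. Their number is not given and is probably small.

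Per affected-type record, the mean excess ranges from about 1 day (visit within 14 days of the stop) through 5 days (28) and 16 days (56) to 70 days (uniform over 24 weeks). All of these rest on the assumed delay. The 70-day figure is the result for reporting at the next scheduled visit and should not be read as the expected size.

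A reader might infer a threat to the non-inferiority conclusion. The documents do not support that: the primary analysis is independent of drug intake. The effect on the 3-point MACE sensitivity analyses cannot be sized without the number of partial dates and the delay to the visit. The point is worth correcting because the correction is cheap and removes an avoidable error from the on-treatment results.

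**What to change.** Define the respective visit in SAP 6.6, and replace the two sentences on partial or missing last-dose dates with:

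> If month and year are known, use the last day of that month; if only the year is known, use 31 December of that year; in each case not later than the respective visit date (if available) or the date of death. Use the visit date only when the date is completely missing.

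When the visit falls in the recorded month, the cap returns the visit date, so those records do not change. Records without a visit date keep the SAP's present month-end fallback, and year-only dates are covered explicitly. The rules for patients lost to follow-up and for deaths in the treatment phase can stay.

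The cost is a few sentences and a small change to the derivation before database lock. The remaining imputation error is at most about 30 days when the month is known, and can be longer for year-only dates. In both cases it lengthens rather than shortens the on-treatment period.

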Data recorded on entry into the study and at randomization will be summarized and compared using univariate descriptive statistics.

Additional analyses will be explored in ~~specific~~ subgroups, e.g. depending on characteristics at baseline with respect to the primary and key secondary endpoints. **Examples of Covariates that will be explored include:**

- Region (North America, Europe, Asia etc.)
- Age (<65,  $\geq$  65 years)
- Systolic and diastolic blood pressure ( $<140$  and  $<90$  mmHg,  $\geq 140$  or  $\geq 90$  mmHg)
- Gender (male, female)
- Prior anti-diabetic treatment (~~none, monotherapy, combination therapy~~ **insulin, no insulin**)
- eGFR  $< 60$  mL/min/1.73 m^2 at baseline
- **Prevalent kidney disease defined as eGFR  $< 60$  mL/min/1.73 m^2 at baseline and/or UACR  $> 300$  mg/g creatinine at baseline**

Further details will be given in the trial statistical analysis plan (TSAP).

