### 6. GENERAL ANALYSIS DEFINITIONS

#### 6.1 TREATMENTS

[figure not shown]
The following treatments are investigated in this trial:

Table 6.1: 1 Treatments and labels used in the analysis

Tre	eatment	Short label
A	Linagliptin 5 mg	Lina
В	Placebo	Placebo

Study intervals are defined in the following figure:

Figure 6.1: 1 Study intervals

Refer to Section 6.6, in case of missing information in eCRF.

During the study treatment phase, patients are allowed to go off trial medication and subsequently re-start trial medication. This may not happen or may happen repeatedly for a given patient, as this trial is expected to go on for a number of years. This is reflected by the off-treatment phase.

For specific safety and efficacy parameters, the duration of the on-treatment phase is given in Section 6.7.2 and Section 7.8.1.1.

Patients will be analysed as randomized for all analyses (safety and efficacy).

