#### Statistical methods

For the primary analysis, a Cox proportional hazard regression model will be performed to compare the effect of linagliptin versus placebo. The model will include randomised treatment and geographical region as factors. Breslow's method will be used for dealing with ties. The SAS PHREG procedure will be used.

The hypothesis of non-inferiority will be tested at the one-sided significance level of  $\alpha_1$ =2.5%.

The hazard function of an event for patient j at time t is assumed to have the form:

$$h_i(t) = \exp(\beta_1 x 1_i + \beta_2 x 2_i) h_0(t), j=1,...,n,$$

where

- $\circ$  h0(t) is the non-negative baseline hazard function for a patient with a value of zero for the explanatory value  $x1_i$  and  $x2_i$
- o β1 is the (unknown) coefficient of the explanatory variable x1
- $\circ$  x1j is an indicator variable representing the treatment group for patient j=1,...,n

- o β2 is the (unknown) coefficient of the explanatory variable x2
- o x2j is an indicator variable representing the geographical region for patient j=1,...,n

The hazard ratio (HR) for the effect of treatment (linagliptin vs. placebo), adjusted for geographical region, will be presented with the 95% confidence interval, the 99% confidence interval and the p-values based on the Wald Chi-Square statistic: one-sided p-value for the non-inferiority test (NI margin 1.3), the one-sided p-value for the superiority test and the two-sided p-value.

Non-inferiority of the primary endpoint will be investigated by comparing the upper limit of the two sided 95% confidence interval of the hazard ratio with the non-inferiority margin of 1.3: if the upper limit is less than 1.3, non-inferiority has been demonstrated.

In case non-inferiority of the primary endpoint is demonstrated, then superiority of the primary endpoint and superiority of the key secondary endpoint will be investigated:

For the final analysis, the first hypothesis (non-inferiority of the primary endpoint) will be tested at the one-sided alpha-level of 2.5%. In case of significance, the null hypothesis is rejected in a confirmatory sense and the next set of hypotheses (two separate hypothesis tests) will be tested: a) test of the primary endpoint for superiority and b) test of the composite renal endpoint for superiority.

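### Setting a year-only birth date to 01 January overstates age for those patients and can move them only upwards across the 65-year cut; 01 July would remove the one-sided shift (minor)

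*SAP*

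**What the plan says.** SAP Section 6.6 (Handling of missing data and outliers), under missing information on the birth date, has one rule: "If only the year of birth is known, the day and month of birth will be imputed as 01 January". The readable text has no rule for a birth date that has month and year but no day.

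The next rule in Section 6.6, on concomitant therapy dates, takes another approach: "For incomplete date information always the midpoint of the possible interval will be used". Under it a year-only date becomes 01 July, and a date lacking only the day becomes the 15th. Other dates in the section have their own conventions. A year-only non-fatal outcome event is set to 01 January but not before randomisation, and incomplete adverse event dates use first-possible and last-possible dates.

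Protocol Section 7.3 names age under 65 against 65 and over among the subgroups to be explored, "depending on characteristics at baseline with respect to the primary and key secondary endpoints". The list is given as examples, with details left to the SAP. SAP Section 7.8.1.1 refers to Section 6.4 for adverse event subgroups, and Section 6.4 is not in the public text. SAP Section 7 also plans baseline summaries of screened patients by age group for EudraCT.

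On the primary Cox model, SAP Section 7.4.1 states: "The model will include randomised treatment and geographical region as factors". Age is not a covariate. Section 7.5.1 analyses the key secondary endpoint in the same way.

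**The concern.** An imputed date at one end of the possible interval gives an error of one sign. A birthday of 01 January can be too early but never too late, so age can be too high but never too low. Such an error does not average out over patients.

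It matters most at a fixed cut. A patient who is 64 at baseline and turns 65 later in that calendar year is counted as 65 if only the year of birth is recorded. No patient is moved the other way. The reported age of year-only patients would be too high, and the older subgroup would include some patients who do not meet its definition. The section gives no reason for choosing the boundary date for birth dates.

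**Working it through.** The documents give no figure on this point, so there is nothing to reproduce. The check has four steps.

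**Inputs**
- From the documents: the 01 January rule and the 01 July comparison (SAP 6.6), the cut at 65 (Protocol 7.3), about 7000 randomised patients (Protocol 7.6), and the MDRD age exponent of -0.203 (Protocol 5.2.3.1).
- Assumed: birthdays uniform over the year; baseline age normal, with mean/SD of 60/10, 65/9, 66/9 or 70/8; reference (visit) dates spread over a 2.5-year window; subgroup age derived from the imputed birth date; 1%, 10% or 100% of patients year-only.

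**Step 1: error in age among year-only patients.** The error is the true day of the year minus the imputed day, enumerated over all days.

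| Rule | Year length | Mean error (days) | Range (days) | Mean absolute error (days) |
|---|---|---|---|---|
| 01 January | 365 | +182.0 | 0 to 364 | 182.0 |
| 01 January | 366 | +182.5 | 0 to 365 | 182.5 |
| 01 July | 365 | +1.0 | -181 to 183 | 91.3 |
| 01 July | 366 | +0.5 | -182 to 183 | 91.5 |

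The mean under 01 January is 182.0/30.4375 = 5.98 months (6.00 in a leap year).

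**Step 2: movement across 65.** The share moved is about the density of age near 65 times the chance that the birthday falls after the reference date. For mean 65 and SD 9 the density at 65 is 0.3989/9 = 0.0443 per year. With visits spread evenly over the calendar year that chance is 0.5, giving 0.0443 × 0.5 = 2.2%. The simulated 2.5-year window covers three first halves and two second halves of a year. Its mean position in the year is (3 × 0.25 + 2 × 0.75)/5 = 0.45, so the chance is 0.55 and the share is 0.0443 × 0.55 = 2.4%.

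The simulation (2 million patients per row) gives, as a percentage of year-only patients:

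| Mean/SD | 01 Jan: up | 01 Jan: down | 01 July: up | 01 July: down |
|---|---|---|---|---|
| 60/10 | 1.98 | 0 | 0.37 | 0.52 |
| 65/9 | 2.43 | 0 | 0.45 | 0.66 |
| 66/9 | 2.43 | 0 | 0.46 | 0.65 |
| 70/8 | 2.20 | 0 | 0.41 | 0.61 |

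The total misplaced is therefore 2.0% to 2.4% under 01 January and 0.9% to 1.1% under 01 July (for example 0.37 + 0.52 = 0.89 and 0.45 + 0.66 = 1.11). I re-ran the four cases with visits spread evenly over a calendar year. The upward share was then 1.8% to 2.2%, and the 01 July errors were nearly equal in the two directions (0.42% to 0.57% each).

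**Step 3: scale for the trial**, at about 2.2% of year-only patients.

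| Year-only share | Patients moved | Shift in trial-wide mean age (years) |
|---|---|---|
| 1% | 7000 × 0.01 × 0.022 = 1.5, about 2 | 0.01 × 0.5 = 0.005 |
| 10% | 7000 × 0.10 × 0.022 = 15.4, about 15 | 0.10 × 0.5 = 0.05 |
| 100% | 7000 × 1.00 × 0.022 = 154 | 1.00 × 0.5 = 0.5 |

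**Step 4: eGFR.** If the imputed age entered the MDRD formula, half a year at age 65 would multiply eGFR by (65.5/65)^-0.203 = 0.9984, a change of -0.16%. A full year gives (66/65)^-0.203 = 0.9969, or -0.31%.

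**The case against.** The strongest case against is that this is a contingency rule, fixed in advance, that may apply to few patients or none. That stands: the documents give no count, and at 1% year-only about two patients change subgroup.

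It is also true that the route to the subgroup is inferred. The readable SAP does not show how age is derived, Section 6.4 is not public, and the protocol offers the age split as an example. The subgroup figures are conditional on that.

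A reader might infer that the SAP contradicts itself because the neighbouring rule uses the midpoint. The documents do not support this. The midpoint rule is confined to concomitant therapy dates, and the same section uses 01 January for year-only outcome events. The neighbouring rule shows only that a centred convention is already in use.

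A reader might also infer that the treatment comparison is biased. It is not. The rule acts on a baseline variable without regard to arm, patients are analysed as randomised (SAP 6.1), and age is in neither confirmatory Cox model.

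Finally, 01 July still misplaces about 1% of year-only patients, and its two directions balance only approximately. That is correct, but the total is about half as large and no longer one-sided. None of these arguments gives a reason to prefer 01 January for a birth date.

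**Conclusion.** The point holds as a minor one, limited to patients with only a year of birth recorded. Given uniform birthdays, their age is overstated by about 6 months on average and never understated. If subgroup age comes from the imputed date, about 2% of them can move into the older group and none out of it. The exact share depends on the assumed age distribution and on when in the year patients are seen.

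It would be wrong to read this as six months added to the age of the whole trial population: that would require every patient to be year-only, which the documents do not suggest. The consequence is confined to descriptive age and a slightly blurred definition of an exploratory subgroup. The non-inferiority test, both superiority tests and all between-arm contrasts are unaffected, and the possible change in eGFR is too small to matter.

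**What to change.** In the birth-date rule of SAP Section 6.6, replace 01 January by 01 July. This follows the convention the section already applies to year-only concomitant therapy dates.

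The cost is one word in the SAP and one line of program code. The SAP was last revised on 18 December 2017, so the change needs a further revision before database lock and is best made together with any other edits. No confirmatory analysis is affected.

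Two optional additions would complete the rule: use the 15th when only the day of birth is missing, which the current text does not cover, and report the number of year-only patients by arm so that a reader can judge the size. If the sponsor prefers to keep 01 January, a sentence giving the reason, together with that count, would be enough.
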